4.1.5 Not currently receiving any chemotherapy

4.1.6 Have previously received platinum- and/or taxane-based chemotherapy treatments and have persistent pain at least 3 months after completion of treatments.

- 4.1.7 Willing and able to comply with study procedures and visit schedule.
- 4.1.8 Willing to abstain from all tobacco/nicotine product use during study treatment and 30-day follow-up period.
- 4.1.9 Ability to self-apply or have the patch applied at home daily.
- 4.1.10 Ability to understand and the willingness to sign a written informed consent document

4.2 Exclusion Criteria

A patient who meets any of the following exclusion criteria is ineligible to participate in the study.

4.2.1 History of pre-existing peripheral sensory neuropathies related to the following:

- Autoimmune disease
- B12/folate deficiency
- Diabetes Mellitus
- Human immunodeficiency virus (HIV)
- Hyper/hypothyroidism
- Monoclonal gammopathy of undetermined significance or multiple myeloma

4.2.2 History of receiving other types of neurotoxic chemotherapy drugs (eg, vinca alkaloids, bortezomib, thalidomide)

4.2.3 Current or prior pheochromocytoma

4.2.4 History of or active or clinically significant cardiac disease including any of the following:

- Unstable angina (eg, anginal symptoms at rest) or onset of angina within 3 months prior to initiating study treatment
- Myocardial infarction diagnosed within 6 months prior to initiating study treatment
- Cardiac arrhythmias requiring anti-arrhythmic therapy other than beta blockers

4.2.5 New York Heart Association (NYHA) class III or IV congestive heart failure (see [Appendix 2](#))

4.2.6 Poorly controlled high or low blood pressure defined as:

- SBP \geq 140; DBP \geq 90

- SBP ≤ 90; DBP ≤ 60

4.2.7 Regular use of the following medications:

- Varenicline
- Bupropion (ie, bupropion hydrochloride sustained release)

4.2.8 Women will be excluded if they are breastfeeding or are pregnant (by urinalysis) within 14 days prior to the start of nicotine transdermal patch administration.

4.2.9 Medical, psychological, or social condition that, in the opinion of the investigator, may increase the patient's risk or limit the patient's adherence with study requirements

5 STUDY ENTRY AND WITHDRAWAL PROCEDURES

5.1 Study Entry Procedures

5.1.1 Required Pre-Registration Screening Tests and Procedures

Refer to the study calendar in [Section 12](#) for the screening tests and procedures that are required prior to registration.

5.1.2 Study Enrollment

The following documents are required for patient registration:

- Completed registration cover sheet
- Completed, signed, and dated eligibility checklist
- Signed and dated consent form

The registrar will complete the registration process by assigning a study identification (ID) number and forwarding the "Confirmation of Registration" form to the registering study team.

No patient may begin study treatment until the Confirmation of Registration assigning a study ID number has been received from the registrar. The registering study team will enter the patient's initial enrollment data (eg, demographics, consent, eligibility, on study) into the OnCore database within 24 hours following study registration (before treatment begins).

5.2 Study Withdrawal

A patient may decide to withdraw from study participation at any time. Patients must be withdrawn from the study when any of the following occurs:

- The patient has withdrawn consent for study treatment and study procedures.
- If, in the investigator's opinion, continuation of the study requirements would be harmful to the patient's well-being.
- The patient is lost to follow-up.

The reason for and date associated with study withdrawal or removal from the study must be documented in the source documents and OnCore database.

6 STUDY TREATMENT

6.1 Baseline Tests and Procedures

Refer to the study calendar in [Section 12](#) for requirements prior to initiation of treatment administration. Initiation of study treatment should begin as soon as possible following study registration. Patients who are eligible and enrolled in the study but do not immediately initiate study treatment are expected to meet eligibility criteria until the time when treatment is initiated.

6.2 Investigational Agent Administration

6.2.1 Nicotine Transdermal Patch Administration and Treatment Schedule:

- Each patient will complete two 14-day treatment conditions, one each for 7 mg and 14 mg nicotine transdermal patch administration with a washout period in between (\geq 14 days and up to 21 days).
- Nicotine transdermal patch administration will begin on Cycle 1, Day 1 (7mg) and Cycle 2, Day 1 (14mg).
- Nicotine transdermal patches will be applied once daily for 14 consecutive days.
- Nicotine transdermal patches will be removed for at least 14 days and up to 21 days at the end of Cycle 1, Day 14.
- Patients will be instructed as follows:
 - Apply the nicotine transdermal patch to dry, clean, hairless skin
 - Patients should apply and remove the nicotine transdermal patch at the same time everyday
 - Patients should wear the nicotine transdermal patch for at least 16 hours per day.

6.2.2 Missed Doses

Patients will be instructed to apply the nicotine transdermal patch on the same day, as soon as they remember, with the following considerations:

- Patients should still remove the missed nicotine transdermal patch at the planned daily removal time.
- Patients should not apply more than one nicotine transdermal patch per day.

6.3 General Concomitant Medication and Supportive Care Guidelines

Nicotine transdermal patch-related symptoms experienced by non-smokers include nausea, dizziness, vomiting, minor skin irritations, and palpitations ([23](#)). These common side effects associated with nicotine administration can occur more commonly in patients with no nicotine use history (ie, never-smokers, nicotine naive patients). The published side effects for a 15mg or less nicotine transdermal patch have been reported as mild and tolerable ([24-27](#)).

6.3.1 Nausea/Vomiting

Management of nausea and vomiting will include anti-nausea medication to reduce the risk of grade 3 nausea or nicotine transdermal patch discontinuation. Anti-emetics should be prescribed as clinically indicated.

6.4 Duration of Therapy

Treatment will continue until any of the following occurs (also see information regarding study withdrawal in Section [5.2](#)):

- AE that requires discontinuation of study treatment (See Section [7.2.2](#))
- Pregnancy
- Patient decision to discontinue study treatment or withdraw from the study
- Investigator determination that discontinuation is in the patient's best medical interest
- Patient non-compliance with the required study treatment visits such that the patient has not been present for more than 60% of the visits (≥ 3 out of 5 visits)
- Inability to initiate Cycle 2 within 21 days after completion of Cycle 1

6.5 Follow-Up Period

During the 30-day follow-up period, patients will be evaluated by the study team at least once. They will be assessed for nicotine serum levels, pain (BPI-SF), global impression of change, CIPN PROs, and AEs.

6.6 Extended (90-day) Follow-Up Period

The extended (90-day) follow-up period will begin at the end of Cycle 2, Day 14 after the last nicotine transdermal patch is removed. The 90-day follow-up will consist of a phone call to patients once at the end of the 90-day follow-up period. Patients will be asked if they have continued to use the nicotine transdermal patch to lessen their CIPN symptoms and if they have developed a dependence to nicotine in any form (eg, cigarettes, electronic cigarettes, smokeless tobacco, or other nicotine-containing products).

6.7 Monitoring Patient Compliance

Patients will be instructed to record the time of their daily self-administration and removal of the nicotine transdermal patch in the study drug diary that will be provided. This record will also document the number of nicotine transdermal patches used during each treatment cycle. Patients will be instructed to bring their diary and any unused drug supply to each visit with the study team.

Patient reports of self-administration and review of the study drug diary will be used to assess the patient's compliance with the nicotine transdermal patch study treatment regimen.

7 MISSED DOSES

Dose reductions or dose omissions will not occur.

7.1 Recording Missed Doses

All missed doses will be recorded in the source documents and captured in the OnCore database.

7.2 General Instructions and Guidelines

7.2.1 Missed Doses

- If a nicotine transdermal patch is missed for an entire 24-hour period, the transdermal patch is omitted, not made up.
- If a nicotine transdermal patch is missed for less than a 24-hour period, the transdermal patch is applied for the remaining hours of the 24-hour period, if possible.

7.2.2 Required Discontinuation of Study Treatment

Nicotine transdermal patch administration will be discontinued if clinically significant toxicities or qualifying toxicities that are related to nicotine transdermal patch therapy occur (See Section [8.1.6](#) for Qualifying Toxicities).

8 ADVERSE EVENTS: DEFINITIONS AND REPORTING REQUIREMENTS

8.1 Definitions

8.1.1 Adverse Event (AE)

AE means any untoward medical occurrence associated with the use of a drug in humans, whether or not considered drug related.

8.1.2 Suspected Adverse Reaction (SAR)

Any AE for which there is a reasonable possibility that the drug caused the AE. “Reasonable possibility” means that there is evidence to suggest a causal relationship between the drug and the AE.

An AE with an attribution of possible, probable, or definite (see Section [8.1.9](#) below) is a SAR.

8.1.3 Serious AE (SAE) or Serious SAR (SSAR)

An AE or SAR is considered “serious” if, in the view of either the investigator or sponsor, it results in any of the following outcomes:

- death,
- a life-threatening AE (An AE or SAR is considered “life-threatening” if, in the view of either the investigator or sponsor, its occurrence places the patient or subject at immediate risk of death. It does not include an AE or SAR that, had it occurred in a more severe form, might have caused death.),
- inpatient hospitalization or prolongation of existing hospitalization,

Planned inpatient hospitalizations are exempt from SAE reporting. Events that prolong hospitalization beyond the expected period of time and otherwise meet reporting criteria are, however, subject to SAE reporting requirements.

- a persistent or significant incapacity or substantial disruption of the ability to conduct normal life functions, or
- a congenital anomaly/birth defect.

Important medical events that may not result in death, be life-threatening, or require hospitalization may be considered serious when, based upon appropriate medical judgment, they may jeopardize the patient or subject and may require medical or surgical intervention to prevent one of the outcomes listed in this definition.

8.1.4 Unexpected SAR

A SAR is considered “unexpected” if

- it is not listed in the investigator brochure or is not listed at the specificity or severity that has been observed;
- or, if an investigator brochure is not required or available, is not consistent with the risk information described in the general investigational plan or elsewhere in the current application, as amended.

“Unexpected” as used in this definition, also refers to SARs that are mentioned in the investigator brochure as occurring with a class of drugs or as anticipated from the pharmacological properties of the drug, but are not specifically mentioned as occurring with the particular drug under investigation.

8.1.5 Unanticipated Problem (UP)

UPs include any incident, experience, or outcome that meets all of the following criteria:

- unexpected (in terms of nature, severity, frequency) given (a) the research procedures that are described in the protocol-related documents, such as the IRB-approved research protocol and informed consent document; and (b) the characteristics of the subject population being studied;
- related or possibly related to participation in the research (possibly related means there is a reasonable possibility that the incident, experience, or outcome may have been caused by the procedures involved in the research); and
- suggests that the research places subjects or others at a greater risk of harm (including physical, psychological, economic, or social harm) than was previously known or recognized.

8.1.6 Qualifying Toxicities

The following nicotine-related toxicities listed below are considered qualifying toxicities and will be used to ensure patient safety and tolerability. The following toxic event as defined per CTCAE v5.0 will be counted toward the stopping rules (See Section [13.3](#)).

- Grade 3 nausea
- Grade 3 vomiting
- Grade 3 dizziness
- Grade 3 pruritus
- Grade 3 headache
- Grade 2 heart palpitations

8.1.7 AE Description and Grade

The descriptions and grading scales found in the revised Common Terminology Criteria for Adverse Events (CTCAE) version 5.0 will be utilized for AE reporting.

8.1.8 AE Expectedness

AEs can be ‘Unexpected’ or ‘Expected’.

Expected AEs are listed in Section [8.2](#) below.

Unexpected AEs are those AEs occurring in one or more subjects participating in the research protocol, the nature, severity, or frequency of which is not consistent with either:

- The known or foreseeable risk of AEs associated with the procedures involved in the research that are described in (a) the protocol-related document, such as the IRB-approved research protocol, any applicable investigator brochure, and the current IRB-approved informed consent document, and other relevant sources of information, such as product labeling and package inserts; or
- The expected natural progression of any underlying disease, disorder, or condition of the subject(s) experiencing the AE and the subject’s predisposing risk factor profile for the AE.

8.1.9 AE Attribution

- Definite – The AE *is clearly related* to the study treatment.
- Probable – The AE *is likely related* to the study treatment.
- Possible – The AE *may be related* to the study treatment.
- Unlikely – The AE *is doubtfully related* to the study treatment.
- Unrelated – The AE *is clearly NOT related* to the study treatment.

8.2 Known AEs List

The expected AEs for a nicotine transdermal patch can be found in Section [9.1.9](#)

8.3 Time Period and Grade of AE Capture

All AE’s regardless of grade or attribution will be recorded from the beginning of study treatment (Cycle 1, Day 1 of nicotine transdermal patch administration) through the 30-day follow-up period. AE assessment may be shortened if the patient goes off study.

Qualifying toxicities will be captured and recorded from the beginning of study treatment (Cycle 1, Day 1 of nicotine transdermal patch administration) through the 30-day follow-up Day 8 - Day 15 study visit. Qualifying toxicity assessment may be shortened if the patient goes off study.

8.4 Procedures for Recording Events

All AEs, SAEs, UPs, and qualifying toxicities will be recorded in MCC's OnCore Clinical Trials Management System. In most cases, it is acceptable to record in OnCore only the highest grade of a toxicity occurring during a particular study segment when an event has serial fluctuations in grade over time.

- Refer to the study calendar in Section [12](#) for the AE assessment schedule.
- AEs will be recorded using the OnCore AE eCRF.
- SAE's will be entered into the OnCore SAE domain. For all SAEs, a corresponding entry should be made in the routine AE record to match the event entries in the SAE domain.
- UPs will be entered into the OnCore Deviations domain.

Note: An SAE that is both an SAE and a UP will be entered in both domains

8.5 Expedited Reporting Procedures for SAEs, SSARs, UPs, and Qualifying Toxicities

Refer to [Table 1](#) for expedited reporting requirement and instructions.

Table 1. Expedited Reporting Requirements (Events, Report Recipients, and Time Frames)

[figure not shown]
SAEs ¹	UPs ²	SSARs ¹	Qualifying Toxicities ³
[REDACTED]	[REDACTED]	[REDACTED]	[REDACTED]
[REDACTED]	[REDACTED]	[REDACTED]	[REDACTED]
[REDACTED]	[REDACTED]	[REDACTED]	[REDACTED]
	[REDACTED]		
	[REDACTED]		

[figure not shown]
1. Report event within 1 business days of becoming aware of the occurrence. A PDF of a de-identified OnCore SAE may be used for expedited event reporting purposes.

2. Report event within 1 business days of becoming aware of the occurrence. A PDF of a de-identified OnCore SAE and/or deviation record may be used for expedited event reporting purposes.

3. Report event by email within 1 business day. See Section [8.1.6](#) and [13.3](#).

4. Each UP must be reported to the VCU IRB within 5 business days of becoming aware of the occurrence.

9.1.9 Adverse Events

Nicotine transdermal patches can cause the following side effects:

9.1.9.1 Common side effects:

- Dizziness
- Headache
- Itching
- Nausea
- Rapid heartbeat
- Skin irritation

9.1.9.2 Less common side effects:

- Constipation
- Drowsiness
- Stomach cramps

9.1.9.3 Uncommon/rare side effects:

- Atrial Fibrillation
- Hives
- Seizures
- Trouble breathing

10 MEASUREMENT OF EFFECT

10.1 Evaluation of Transdermal Nicotine Patch Efficacy

CIPN PROs will be measured using the EORTC QLQ-CIPN20 sensory subscale score. The QLQ-CIPN20 numerical score has a range of 19-76, in which lower scores indicate less symptoms and a better quality of life. The scores can also be converted to a scale of 0 to 100, in which higher scores indicate less symptoms and better quality of life. A recently published study provides validity and guidance as to how to interpret QLQ-CIPN20 scores (18). Utilizing this study's reported numerical relationship between QLQ-CIPN20 scores and peripheral sensory neuropathy CTCAE grades (initially reported using CTCAE grade v4.0) as a hypothetical guide (See [Table 2](#)), we can estimate how many QLQ-CIPN20 score points are needed to decrease the CTCAE score by 1 grade. Using the 19-76 numerical scale for QLQ-CIPN20, a minimum decrease of 2.7 points (range of 2.7-5.6 points) would be required to improve a patient's quality of life by one grade (grade 2 to grade 1).

Table 2. Reported/Suggested Numerical Relationship Between CTCAE v4.0/v5.0 and EORTC QLQ-CIPN-20 Scores.

Peripheral Sensory Neuropathy CTCAE v5.0	EORTC QLQ-CIPN20 (Scale 19-76)
Grade 0	21.6
Grade 1	24.3
Grade 2	29.9
Grade 3	33.6

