The clinical trial will yield several important results. First, using an acute nicotine transdermal patch administration will determine both the potential efficacy and feasibility of using nicotine as a potential treatment for neuropathic pain associated with CIPN. Additionally, if nicotine appears to have a positive treatment effect, as defined by a ≥ 2.7 point decrease in patient’s total sensory score (baseline compared to treatment and post-treatment scores) of the QLQ-CIPN-20 questionnaire (eg, an improvement in the patients quality of life by one grade), future randomized clinical trials comparing nicotine to other commonly prescribed treatments, such as duloxetine, may be warranted. In addition, further studies of subtype receptor selective agents or of patient population subgroups (based on smoking history, gender, chemotherapeutic agents, or receptor expression level) can be designed.

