13.1 Sample Size and Accrual

Using the 19-76 numerical scale for QLQ-CIPN220, a minimum decrease of 2.7 points (range of 2.7 – 5.6 points) would be required to improve the patient's quality of life by one grade (grade 2 to grade 1). A sample size of 47 would provide a power of at least 95% to detect a minimum change of 2.7 EORTC QLQ-CIPN20 scale points, assuming a moderately sized effect (ie, effect size 0.54) and 5% level of significance. Assuming 10% dropout or non-compliance, this will bring the total size to 52 patients. Recruitment ends when the required number of evaluable patients to complete the study is reached. A patient is evaluable if pain scores are available for the patient with each dose level. This still might have missing values due to non-compliance. All of the patients will be included in the final analysis and subjects with missing values will be included based on imputation-based method provided the amount of missing values is not excessive. If final data contains patients with more than 50% missing observations, we will use a pattern mixture model for imputation of missing data followed by longitudinal data.

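### The 2.7-point efficacy threshold is labelled as the Grade 2 to Grade 1 step, but the plan's own Table 2 puts that step at 5.6 points

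*Combined protocol and SAP*

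**What the plan says.** Section 10.1 uses a published relationship between QLQ-CIPN20 scores and CTCAE sensory neuropathy grades, "as a hypothetical guide", and says that from it "we can estimate how many QLQ-CIPN20 score points are needed to decrease the CTCAE score by 1 grade". It concludes that "a minimum decrease of 2.7 points (range of 2.7-5.6 points) would be required to improve a" given patient by one grade, and it names that step as Grade 2 to Grade 1. Table 2, placed directly after this, lists one score per grade on the 19 to 76 scale: Grade 0, 21.6; Grade 1, 24.3; Grade 2, 29.9; Grade 3, 33.6.

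Section 13.1 (Sample Size and Accrual) repeats the claim, "quality of life by one grade (grade 2 to grade 1). A sample size of 47 would provide", and sizes the trial "to detect a minimum change of 2.7 EORTC QLQ-CIPN20 scale points".

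Section 3.2 defines efficacy in the primary endpoint as a fall of at least 2.7 points and glosses this as one grade. Section 1.3 describes a positive effect as a "decrease in patient’s total sensory score (baseline compared to treatment and post-treatment scores") of that size, "of the QLQ-CIPN-20 questionnaire (eg, an improvement in the patients quality of life by one grade), future randomized clinical trials" possibly being warranted as a result. Section 4.1.2 admits only patients above CTCAE Grade 1, with a sensory score of at least 24.3.

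**The concern.** The sentence names one transition, Grade 2 to Grade 1, and attaches to it a figure that the adjacent table gives for a different one. The named transition is the relevant one for the trial, because nobody graded 1 by CTCAE can enter. The figure attached to it belongs to Grade 1 to 0, which is not the first one-grade improvement for a patient entering at Grade 2 or 3.

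The consequence lies in what a result would mean. The 2.7 points serve as the threshold in the primary endpoint, the trigger for considering randomized trials, and the planning difference. The one-grade link is the only clinical reason the documents give for 2.7. If the text stands, a fall of 2.7 points can be described as a one-grade improvement when Table 2 puts it at about half of the Grade 2 to 1 step.

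**Working it through.** **Inputs.** Table 2 (Section 10.1): 21.6, 24.3, 29.9 and 33.6 for Grades 0 to 3. Entry above Grade 1 and score of at least 24.3 (Section 4.1.2). n = 47, effect size 0.54, 5% level, power at least 95% (Section 13.1, Sample Size and Accrual). One-sided matched paired t-test (Section 13.2.1). The plan states no SD.

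**1. Reproduce the plan's range.** Differences between adjacent Table 2 scores:

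| Step | Subtraction | Points |
|---|---|---|
| Grade 1 to 0 | 24.3 − 21.6 | 2.7 |
| Grade 2 to 1 | 29.9 − 24.3 | 5.6 |
| Grade 3 to 2 | 33.6 − 29.9 | 3.7 |

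The smallest and largest are 2.7 and 5.6, so the printed range of 2.7 to 5.6 is reproduced. It spans all three transitions and is not a range for Grade 2 to 1. That the range reproduces also makes a misread table unlikely.

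**2. Test the label.** The plan attaches 2.7 to Grade 2 to 1; the table gives 5.6. An alternative reading, with a cut-off midway between grades, does not rescue it: the Grade 1/2 midpoint is (24.3 + 29.9)/2 = 27.1, and 29.9 − 27.1 = 2.8, not 2.7.

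**3. Size for the enrolled grades.** For entry Grade 2, 2.7/5.6 = 0.48. For entry Grade 3, 2.7/3.7 = 0.73. The range of one-grade steps for these two grades is 3.7 to 5.6. Grade 4 has no Table 2 value, so nothing is said about it.

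**4. Effect on sample size.** The implied SD of change is 2.7/0.54 = 5.0. Power of a paired t-test against zero change, from the noncentral t distribution with 46 degrees of freedom and noncentrality (effect size) × √47:

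| True fall | Effect size | Power, one-sided 5% | Power, two-sided 5% |
|---|---|---|---|
| 2.7 | 0.54 | 0.977 | 0.952 |
| 3.7 | 3.7/5.0 = 0.74 | 0.9996 | 0.9987 |
| 5.6 | 5.6/5.0 = 1.12 | > 0.9999 | > 0.9999 |

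The plan's claim of at least 95% is reproduced. At the same SD a larger target only raises power.

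**5. If 2.7 is a patient-level threshold.** Assume normally distributed changes, SD 5.0 and a true mean fall of 2.7. The share of patients falling by at least *x* is P(Z ≥ (*x* − 2.7)/5.0):

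- *x* = 2.7: P(Z ≥ 0) = 50%, which follows from the assumed mean
- *x* = 3.7: P(Z ≥ 0.20) = 42%
- *x* = 5.6: P(Z ≥ 0.58) = 28%

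**The case against.** The subtraction is not in dispute; the case on the other side concerns weight and reach.

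- **The plan hedges.** Table 2 is offered as a hypothetical guide and its title says reported or suggested; Sections 1.3 and 3.2 introduce the one-grade gloss with eg. Read as the smallest step anywhere in the table, 2.7 is right. This limits how exact the mapping can be, but the sentence still names a specific transition, and names the wrong one.
- **The primary analysis has no threshold.** Section 13.2.1 tests for a decrease with a paired t-test, and no analysis section converts scores to grades. That is so, and it is why test, sample size and power stand. But Section 3.2 puts 2.7 in the definition of efficacy, so the interpretation is affected.
- **Grades could be bands.** With midpoint cut-offs, a patient at 33.6 would need only 33.6 − 31.75 = 1.85 points to leave Grade 3, and one at 29.9 would need 2.8. The plan states no cut-offs, and its own range uses adjacent differences. What stands is that no claim should be made about the grade of an individual score.
- **The entry score floor is 24.3.** A patient there who falls 2.7 reaches 21.6, a full Table 2 step. But by the table that step is Grade 1 to 0, and the same patient must be above Grade 1 by CTCAE.
- **Effect size 0.54 is another basis.** It is a planning assumption, not a clinical reason for the endpoint threshold.
- **Patient or mean level is a separate question.** Agreed. It is secondary, and the conclusion does not depend on it or on the percentages in step 5.

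**Conclusion.** The label is wrong as written. By the plan's own table the Grade 2 to 1 step is 5.6 points, about twice the 2.7 attached to it. For entry Grades 2 and 3, a 2.7-point fall is 48% and 73% of the one-grade step, so describing it as one grade is not supported when a step is taken, as the plan takes it, as the difference between adjacent Table 2 scores. Because the figure sits in the primary endpoint, it should be corrected before any result is read against it.

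This rests on Table 2 being transcribed correctly from its source, which cannot be checked here. The statement that no more patients are needed rests on the implied SD of 5.0 and applies to a test against zero change. It does not extend to showing that the mean fall exceeds 2.7: if the true fall were 2.7, a trial of 47 would seldom exclude that value. The patient-level shares rest also on normality and a true mean of 2.7.

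**What to change.** Check Table 2 against its source. If it stands:

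1. In Sections 10.1 and 13.1 (Sample Size and Accrual), detach the Grade 2 to 1 label from 2.7 and write, for example: *Taking Table 2 as a hypothetical guide, the one-grade steps are 2.7 points (Grade 1 to 0), 5.6 (Grade 2 to 1) and 3.7 (Grade 3 to 2). The planning difference of 2.7 points is the smallest of these and about half (48%) of the Grade 2 to 1 step.*
2. In Sections 1.3 and 3.2, delete the one-grade gloss, or tie any such statement to 5.6 points (Grade 2 to 1) or 3.7 points (Grade 3 to 2).
3. If 2.7 is kept as threshold and planning difference, add a sentence giving a rationale other than one grade. The documents offer no other clinical rationale, so the study team must supply it.
4. As a related clarification, say in Sections 3.2 and 13.2.1 whether 2.7 applies to each patient (then report the proportion reaching it) or to the mean change (then report the mean with its confidence interval against 2.7). Section 1.3 speaks of the patient's score, while Section 13.1 (Study Design) and Section 13.2.1 give no threshold.

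The cost is one source check and a few sentences. The sample size and the paired t-test stay as they are. The price is a less favourable reading of the threshold, and 2.7 has no stated clinical justification until another is given.
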